8.3.3 Packaging and labeling

Lambda Injection is a sterile, nonpyrogenic, ready-to-use (RTU) solution (0.4 mg/mL) that is clear to opalescent, colorless to pale yellow, and essentially free of particles. Lambda Injection is provided in a 1-mL long Type I glass syringe (0.18 mg/syringe) with a staked 29-gauge, 1/2-

inch, thin-walled needle. The syringe has a rigid needle shield and is stoppered with a plunger stopper. Syringes are prefilled with a solution of Peginterferon Lambda-1a drug substance, L-histidine, mannitol, polysorbate 80, hydrochloric acid, and water for injection and for a single use only.

Normal saline injection is a sterile, nonpyrogenic solution that is clear and will be provided in a 1 ml BD plastic syringe with a ½ inch, thin-walled needle with safety shield. Syringes are prefilled with a 0.9% sodium chloride solution and for a single use only. The injection will be prepared by the Stanford Investigational Pharmacy.

8.4 Study drug supply, dosage, administration, and storage

8.4.1 Supply of study drug at the site

Lambda will be shipped by the manufacturer (Eiger BioPharmaceuticals) and stored at the Stanford Health Care Investigational Pharmacy. Normal saline injection will be prepared by the Stanford Health Care Investigational Pharmacy

8.4.2 Dosage

Each participant randomized to receive Lambda will receive a single subcutaneous dose of either 180 mcg Peginterferon Lambda-1a or 0.45 mL normal saline.

8.4.3 Dispensing

Study drug will be dispensed daily by the Stanford Investigational Pharmacy and brought in a cooler to the study clinic for administration.

8.4.4 Administration instructions

Lambda syringes are marked with dose indicator lines, which are used as a reference point for administering the correct dose. The clinician will expel the air bubble from the syringe and set the dose by aligning the front edge of the stopper with the correct dose indicator line. A sufficient overfill is included in each syringe for needle/syringe, dose adjustment, and bubble expulsion losses, leaving a sufficient amount of Lambda Injection for delivery of up to 180 mcg.

Both lambda and normal saline will be administered subcutaneously in either the lateral or posterior aspect of the upper arm or thigh. Injection sites should be clean and free of infection, skin lesions, scars, birthmarks, bony prominences, and large underlying muscles, blood vessels, and nerves. A lifted skinfold technique (pinching or bunching the skin) will be used to lift the subcutaneous layer away from underlying muscle, and the skin will be cleaned with an alcohol-impregnated swab before injection at a 90° angle.

Following study drug administration, participants will be observed in the study clinic for thirty minutes to assess for any adverse events.

8.4.5 Storage

Lambda Injection will be stored in a refrigerator at 2°C to 8°C (36°F to 46°F) and protected from long-term (> 24 hours) exposure to light. Lambda injection should not be frozen.

Normal saline injection will be stored in a refrigerator at 2°C to 8°C.

8.4.6 Study drug accountability

Study drug accountability and monitoring will be performed by the Stanford Health Care Investigational Pharmacy. The Investigational Pharmacy will maintain accurate, complete, and current records of receipt, use, or disposition of study drugs, including: 1) dates of receipt, 2) dates of dispensing, 3) quantities currently maintained for dispensing, 4) name of participant and amount dispensed, and 4) amounts remaining at the end of trial and method of disposition. Medications will be stored in a refrigerator at 2°C to 8°C (36°F to 46°F) and protected from long-term (> 24 hours) exposure to light; refrigerators will have temperature logged.

9 SUBJECT MANAGEMENT

9.1 Subject Follow-up

9.1.1. In home assessments.

Participants will complete an at-home symptom questionnaire by REDcap on each day of follow-up through day 28, including in-home assessments of temperature and O2 saturation. These assessments will be reviewed daily by a clinical research coordinator, and patients will be telephoned by a physician if they report an elevated temperature, diminished O2 sat (<94%), or signs/symptoms of respiratory or cardiopulmonary distress (e.g. shortness of breath, dyspnea on exertion). On each day through day 28, patients will also be instructed to collect an anterior nare swab in a pre-labeled container and to store these specimens in a refrigerator at 2°C to 8°C, and to bring these in to their next scheduled appointment. Prior to the optional follow up visits at months 4, 7 and 10, participants will complete an at-home symptom questionnaire and will be asked to collect a stool specimen to bring to their next scheduled appointment.

9.1.2. Follow-up in-clinic assessments.

[figure not shown]
Participants will be seen at follow-up visits at Day 1±1, 3±1, 5±1, 7±1, 10±1, 14±1, 21±1, and 28±1. At each visit, a subjective medical history will be performed, including assessments for use of any concomitant medications. Vital signs will be obtained (temperature, blood pressure, pulse rate per minute, breath rate per minute and oxygen saturation), and oropharyngeal and anterior nare swabs will be collected. Participants will also submit at-home collected anterior nare swab specimens for evaluation. Clinical laboratory measurements will be performed at days 5±1 and 14±1 to assess for safety, with additional clinical laboratory assessments performed as needed for clinical follow-up and/or patient management. Additionally, ~25 mL peripheral blood will be collected from study participants at enrollment and at Days 5±1, 14±1, and 28±1 for processing and cryopreservation into a specimen biobank. Safety and tolerability of Lambda will be assessed by adverse event (AE) monitoring, vital signs assessment and clinical laboratory tests. Patients will reach the end of study at day 28±1 of follow-up. Optional long-term follow up visits will be scheduled 4, 7, and 10 months post-enrollment. The window of ±3 weeks is allowed for these long term follow up visits.

At these long-term follow up visits, patients will undergo a detailed medical history, physical exam and psychosocial assessment, as well as specimen collection for biobank, a 6-minute walk test, and an olfactory assessment using the NIH toolbox. All patients will receive standard supportive care for management of COVID, as defined by clinical practice guidelines:

<https://www.cdc.gov/coronavirus/2019-ncov/hcp/clinical-guidance-management-patients.html>

9.2 Clinical laboratory measurements

All clinical laboratory measurements (CBC and CMP) at enrolment and during follow-up will be performed using point-of-care CLIA-waived devices or in the Stanford Hospital clinical laboratory. Follow-up clinical laboratory assessments will be performed at Day 5 ± 1 and Day 14 ± 1 post randomization, with additional clinical laboratory assessments performed as needed for clinical follow-up and/or patient management. (Fig 4).

9.3 Virologic assessments

Oropharyngeal and anterior nare swabs for SARS-CoV2 RNA will be collected using a standardized technique at all study visits. Additionally, participants will be instructed in collection of anterior nasal swabs at home and asked to collect a swab each day. We will ask participants to collect stool at home (between days 0-3, 10-14, and 21-28; and at 4, 7 and 10 months post-randomization). All swabs will be collected in viral transport media or phosphate buffered saline. Stool will be collected in stabilization tubes, kept at room temperature, and brought to the next study visit. Samples collected in the clinic will be refrigerated and transported the same day to the Stanford clinical virology laboratory for processing. We will ask that swabs collected at home be stored in a 4 degree refrigerator until their study visit, at which point they will be transferred to the study team and transported to the clinical virology laboratory. Fridges will be provided to the participants at enrolment. In the clinical virology laboratory, samples will undergo automated nucleic acid extraction followed by a FDA-cleared quantitative real-time PCR assay for SARS-CoV-2, which will generate both qualitative (positive or negative) and quantitative (estimated viral copies) results. The assay is validated for nasopharyngeal, oropharyngeal, and anterior nare samples. The stool assays have been analytically validated and are undergoing clinical validation.

9.4 Biobanking/Immune phenotyping

We will biobank longitudinal samples collected from patients enrolled in this trial. This will allow for ongoing studies to define the dynamics of the host immune response to COVID-19, with the eventual goal of gaining insight into mechanisms by which control or prevention can be achieved. For biobanking activities, samples will be collected at enrolment, day 5 ± 1 , day 14 ± 1 , and day 28 ± 1 post-randomization, with optional additional biobanking at 4, 7, and 10 months post-randomization (Fig 4). The window of ± 3 weeks is allowed for these long term follow up visits. Stool will be collected as above and biobanked for microbiome assessments.

At the time of blood draw, one 2.5 ml PaxGene tube and two 10 ml CPT (or green-top heparin) tubes will be collected for biobanking and brought to the BSL2+ research lab in Grant S146b. This whole blood then be stored in either stored in specific fixatives, used directly to assess innate immune phenotype and/or the immune response to toll like receptor stimulation, and/or separated into plasma and peripheral blood mononuclear cells (PBMC) using a Ficoll gradient, following standard protocols. All samples will have unique labels with barcodes and unique study identifier. Specimens will be logged into the Stanford Biobank through the OpenSpecimen database tracking system. Plasma will be stored at -80°C for future immunologic and/or pharmacokinetic studies, which may include measurement of levels of cytokines, antibodies, and other features related to the host immune response. PBMCs will be stored in liquid nitrogen to maintain viability, and will be evaluated using flow cytometry, RT-PCR, RNA sequencing, and other assays to assess the host immune response.

In a subset of patients, we will consider a finger stick blood sample at day 14 and/or 28 to collect blood on a dry blood spot to validate performance characteristics of a serologic assay in comparison to venipuncture.

9.5 Reimbursement of subjects

Subjects will receive \$40 for each visit to support transportation costs and inconvenience of frequent visits to the clinic for the first 28 days. For the optional visits at months 4, 7 and 10, subjects will receive \$100 per visit; this is to encourage study retention. Preferred method of payment is gift card after the completion of each study visit. Subjects will receive a thermometer and a pulse oximeter for study use which they may keep after study completion.

9 ADVERSE EVENT REPORTING AND DOCUMENTATION

10.1. Monitoring and Reporting of Adverse Events

10.1.1. Definitions

An adverse event is defined as "any untoward medical occurrence in a patient or clinical investigation subject administered a pharmaceutical product that does not necessarily have a causal relationship with this treatment" (ICH Guidelines E2A). An adverse event can further be broadly defined as any untoward deviation from baseline health, which includes:

- Worsening of conditions present at the onset of the study
- Deterioration due to the primary disease

- Intercurrent illness
- Events related or possibly related to concomitant medications

(International Centers for Tropical Disease Research Network Investigator Manual, Monitoring and Reporting Adverse Events, 2003).

10.1.2. Identification of Adverse Events

At each scheduled and unscheduled visit to the clinic, study clinicians will assess patients according to a standardized case record form. A severity grading scale, based on toxicity grading scales developed by the NIH Divisions of AIDS (DAIDS) Toxicity Tables, will be used to grade severity of all symptoms, physical exam findings, and laboratory results (Appendix 3). All participants, regardless of treatment arm, will be assessed using the same standardized case record form. Adverse event monitoring will occur during the period when study drugs are given and up to 1 month after cessation of study drugs.

Data will be captured on the incidence of all adverse events, regardless of severity. For each adverse event identified and graded as severe or life threatening and felt to be possibly, probably or definitely related to study drugs, an adverse event report form will be completed. In addition, an adverse event form will be completed for all serious adverse events and unexpected events, regardless of severity. An adverse event report form will not be completed for events classified as mild or moderate (unless they are serious or unexpected), as mild and moderate symptoms are common and difficult to distinguish from signs and symptoms due to COVID and other common illnesses. The following information will be recorded for all adverse experiences that are reported:

- 1) Description of event
- 2) Date of event onset
- 3) Date event reported
- 4) Maximum severity of the event
- 5) Maximum suspected relationship of the event to study drugs (either SP or DP)
- 6) Whether the event is a serious adverse event
- 7) Initials of the person reporting the event
- 8) Outcome
- 9) Date event resolved

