8.2 Blinding

Administration of all study drugs will be single-blind (blinded to the study participant). All doses of study drugs will be prepackaged by the investigational pharmacist and administered by a study nurse not involved in data analysis. The study biostatisticians will be blinded to subject randomization, with the exception of an unblinded subgroup who will generate the randomization scheme and perform unblinded interim analyses. The subgroup will not discuss the unblinded data or interim results with the blinded biostatisticians and will save their materials on a server that is inaccessible to the blinded members. This study blind will be broken on completion of the clinical study and after the study database has been locked. During the study, the blind may be broken **only** in emergencies when knowledge of the patient's treatment group is necessary for further patient management. When possible, the Investigator should discuss the emergency with the data safety and monitoring board prior to unblinding.

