10.1.3. Reporting of Adverse Events

Guidelines for reporting of adverse events provided by the Stanford Institutional Review Board and the Food and Drug Administration (FDA) in the U.S. will be followed as summarized in Table 1 below.

Table 1. Guidelines for reporting adverse events

Institution	Type of Adverse Events	When to Report
Stanford IRB	Adverse event that Stanford PI determines: 
 • changes the study risks or benefits, 	
 • Within 10 working days of PI's awareness

	OR necessitates modification to the IRB-approved consent document(s) and/or the IRB-approved application/protocol	
FDA	
 Definitely, Probably or Possibly related AND BOTH Serious* AND Unexpected[‡] 	
 For fatal or life-threatening events, by telephone or fax within 7 calendar days of first awareness All other reportable events within 15 calendar days of first awareness

Serious Adverse Event (SAE) is any AE that results in any of the following outcomes:

- Death,
- Life-threatening adverse experience,
- Inpatient hospitalization or prolongation of existing hospitalization,
- Persistent or significant disability/incapacity,
- Congenital anomaly/birth defect, or cancer, or
- Any other experience that suggests a significant hazard, contraindication, side effect or precaution that **may require medical or surgical intervention** to prevent one of the outcomes listed above,
- Event occurring in a gene therapy study
- Event that changes the risk/benefit ratio of the study.

Unexpected Adverse Event An adverse event is defined as being unexpected if the event exceeds the nature, severity, or frequency described in the protocol, consent form and investigator brochure (when applicable). An unexpected AE also includes any AE that meets any of the following criteria:

- Results in subject withdrawal from study participation,
- Due to an overdose of study medication, or
- Due to a deviation from the study protocol

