11 DATA SAFETY MONITORING

The proposed study will conform to rigorous standard monitoring procedures, standardized reporting of adverse events (Adverse Event Report Forms are completed by study coordinators and sent immediately to the investigators), and review of the study by a Data and Safety Monitoring Board (DSMB) at both an interim and final analysis. The PI has primary responsibility for the overall conduct of the study, including the safety of human subjects. The PI will ensure appropriate (1) conduct of the informed consent process (e.g. that informed consent is obtained before proceeding with study procedures); (2) enrollment of study subjects; (3) collection and analysis of data; (4) implementation of study procedures to ensure consistent monitoring of subjects for possible adverse events; (5) review of adverse events and reporting to the DSMB and the IRBs; and (6) maintenance of the privacy and confidentiality of study subjects. The PI maintains ultimate responsibility for the project and for the safety of study participants. The PI will be in contact with the research team on a regular basis to review the progress of the study and address any human subject issues that occur. These discussions may involve adverse event prevention measures, recruiting of appropriate study subjects, research staff training on protection of human subjects, as well as occurrence of adverse events, unexpected incidents, or protocol problems.

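### For severe adverse events that are neither serious nor unexpected, the report form depends on a relatedness call by clinicians whom the plan does not state to be blinded

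*Protocol*

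**What the plan says.** Protocol 10.1.2 sets two routes to the adverse event report form. The first is for an event "graded as severe or life threatening and felt to be possibly, probably or definitely related to study drugs". The second has no causality condition: "an adverse event form will be completed for all serious adverse events and unexpected events, regardless of severity". Mild and moderate events are exempt unless they are serious or unexpected.

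The same section says, before either route, "Data will be captured on the incidence of all adverse events, regardless of severity". It applies DAIDS severity grading to symptoms, examination findings and laboratory results, and adds that "All participants, regardless of treatment arm, will be assessed using the same standardized case record form". Nine detail items, among them onset date, maximum severity, relationship, outcome and resolution date, come under a narrower heading: "The following information will be recorded for all adverse experiences that are reported".

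Protocol 11 describes what happens to a completed form: "Adverse Event Report Forms are completed by study coordinators and sent immediately to the investigators".

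On blinding, Protocol 8.2 describes drug administration as "single-blind (blinded to the study participant"), and it also blinds the biostatisticians apart from an unblinded subgroup. Section 8.3.2 says that the placebo syringe does not match the active one. Section 4.1 calls the trial open-label.

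**The concern.** Whether a severe event is due to the drug is what a randomised comparison is meant to help answer. A rule that lets one clinician's opinion on that question decide whether the event is fully documented puts the answer ahead of the evidence. If that clinician knows or can guess the arm, the same event could be documented in one arm and not in the other.

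The issue is concrete here because the known effects of the drug resemble the disease. Protocol 2.2 describes transaminase rises, flu-like symptoms, myalgia and fatigue with Lambda, and several of these overlap with COVID-19 symptoms. Section 10.1.2 itself excuses mild and moderate events from the form because they are hard to tell apart from COVID. It then makes the form for some severe events turn on that same distinction, and gives no reason for doing so.

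At stake are the follow-up detail on a subset of severe events, the ability to audit a judgement of unrelated, and how quickly investigators see those events.

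**Working it through.** No arithmetic applies; the check is to read the rules together.

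**Which severe events depend on attribution.** Take an event graded severe or life-threatening and classify it by whether it is serious, unexpected and judged at least possibly related (Protocol 10.1.2 and 10.1.3):

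| Serious | Unexpected | Judged related | Judged unrelated |
|---|---|---|---|
| Yes | Yes | Form | Form |
| Yes | No | Form | Form |
| No | Yes | Form | Form |
| No | No | Form | **No form** |

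Attribution decides only in the last row. The rows are not equally likely, so the table shows where the gap lies and not how large it is.

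**Does the last row include Grade 4?** Section 10.1.3 lists "Life-threatening adverse experience" as serious, which might seem to remove Grade 4 from the row. The DAIDS table in Appendix 3 does not work that way. It labels Grade 4 as potentially life-threatening, says that severity and seriousness are different things, and defines a life-threatening event as an immediate risk of death in the investigator's view. ALT at or above 10 times the upper limit of normal is Grade 4 on the number alone. An asymptomatic rise of that size need not be serious. Most clinical Grade 4 events probably would be.

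**Can events in this row be expected?** Section 10.1.3 calls an event unexpected if it goes beyond the nature, severity or frequency described in the protocol, consent form or investigator brochure. Protocol 2.2 reports Grade 3 or 4 treatment-related events in 7 of 14 patients in a 48-week study at 180 mcg, and ALT or AST increase in 5 (35.7%). Severe events of these types can therefore be argued to be expected. The opposite can also be argued, because at 180 mcg in healthy volunteers the section reports only Grade 1 rises, in one subject (3.3%). The brochure and consent form are not available to settle it.

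**What is lost without the form.** Occurrence and severity grade remain. Chemistry is scheduled at enrolment, day 5 and day 14 (Protocol 9.2), so a laboratory rise is dated to a visit. Daily questionnaires to day 28 (9.1.1) date many symptoms approximately. No other provision requires a relationship call, a formal onset date, an outcome or a resolution date. For a rise first seen at day 14, resolution depends on tests done as needed.

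**Does a planned analysis use the form?** Protocol 12.5 and SAP 2.6 tabulate and compare adverse event frequency by type and arm, with no relatedness filter. They do not depend on the form.

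**Who makes the call?** Section 10.1.2 has study clinicians assess patients. Neither document states that they are blinded.

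**The case against.** The strongest case against the point is that the gap is narrow and touches no planned result. Serious and unexpected events reach the form whatever their cause. An event escapes only if it is judged not even possibly related, which is a low bar for a known liver signal. Incidence, grades, laboratory values and daily symptoms are all collected. The monitoring board reviews safety data on all enrolled patients at the interim (Protocol 11.2), and home assessments are reviewed daily. All of this stands, and it limits the point to documentation and its timing.

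A reader might infer several stronger things that the documents do not support:

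- **That any severe event needs a drug-related verdict to get a form.** The second route in 10.1.2 rules this out.
- **That the relationship field is circular, filled in only after the event has been judged related.** Forms for serious and unexpected events record the relationship for unrelated events too.
- **That the adverse event comparison is biased.** It uses all events, related or not.
- **That 7 of 14 measures the loss.** Those are treatment-related events, which this rule does put on a form, and they come from a 48-week study and not from a single dose.
- **That assessing clinicians know the arm.** Section 8.2 restricts breaking the blind to emergencies and asks the investigator to consult the monitoring board first where possible, which suggests that the investigator may not routinely know it. Against that stand the participant-only definition of the blind, the unmatched syringes and the open-label label. The supportable statement is that blinding of assessors is not established.

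**Conclusion.** The point holds for one class: Grade 3 or higher events that are non-serious, expected and judged unrelated. For these, the plan drops the required relationship call, onset date, outcome and resolution date, and the immediate forwarding to investigators. The judgement that decides this is made by clinicians not stated to be blinded, so the loss could differ by arm, in a direction that cannot be predicted.

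The number of such events cannot be estimated from the documents. No effect on the planned frequency tables or on any efficacy analysis is shown.

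Two assumptions carry the conclusion. The first is that the nine-item list covers only events that have a report form. The wording and position of the list, and its items for the date reported and the reporter's initials, support that reading, but the section does not say so outright. The second is that some severe events will be classed as expected, which depends partly on documents not available here.

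This is a cheap improvement and not a flaw that threatens the trial's conclusions.

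**What to change.** In Protocol 10.1.2, require the report form for every Grade 3 or higher event regardless of attribution, with the relationship recorded on the form. Keep the existing route for serious and unexpected events, and leave the rule for mild and moderate events as it is.

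Two clarifications belong in the same edit. State whether the clinicians who judge relatedness are blinded, and reconcile the open-label description in 4.1 with the single-blind one in 8.2. Correct the relationship item in the nine-item list, which refers to SP or DP; these are not defined in the protocol and are not this trial's treatments.

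The cost is protocol wording and a small number of extra forms among 120 participants. No analysis, sample size or visit schedule changes.
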